8.7.4 Physical examinations

A full physical examination will be performed at Screening, Week 12 and Week 24 whereas a limited physical examination (cardiovascular system and lower extremities oedema only) will be performed at all other visits during the randomisation phase and Week 36.

The number and percentage of patients reporting an abnormal physical examination finding (Abnormal CS and Abnormal NCS) will be presented per body system for each treatment regimen and time-point.

In addition the grade of pitting oedema will be summarised descriptively for each treatment regimen and time-point.

8.7.5 Electrocardiograms

12-Lead ECG assessments will be performed at Screening, Baseline, Week 4, Week 8, Week 12, Week 24 and Week 36.

Descriptive statistics (observed values and changes from baseline) will be presented for the 12-lead ECG measurements for each treatment regimen and time-point for all ECG parameters (Heart Rate, PR interval, QT interval, RR interval, QRS duration and QTcF interval). In addition, the overall ECG interpretation will be summarised by presenting the number and percentage of subjects with “Normal”, “Abnormal, NCS” and “Abnormal, CS” for each treatment regimen and time-point.

8.7.6 DXA Scan

DXA Scan assessments will be performed at screening (up to day 8 after randomisation) and Week 24 and will be over-read by IMI. Both the site assessed and over-read data will be used for all statistical analysis and utilise the visit windows specified in Appendix F. If multiple assessments are recorded within the window, the closest to the target date will be used for analysis.

Descriptive statistics (observed values, changes from baseline and percentage change from baseline) for bone density in both the lumbar spine and hip (total and femoral neck) will be presented. In addition descriptive statistics (observed values and changes from baseline) for the associated T-scores in both the lumbar spine and hip will be presented for each treatment regimen and time-point.

A shift table of baseline severity categories (Normal, Osteopenia and Osteoporosis) to post baseline severities will be generated by treatment regimen and visit.

Change from baseline in bone density (in both the lumbar spine and hip) to Week 24 will be analysed using an ANCOVA model with treatment as a fixed effect and the associated baseline value as a covariate. Least squares means and standard errors will be presented for each visit, p-value and 2-sided 95% confidence interval for treatment differences across all doses will be presented for each visit. Significance tests will be based on least-squares means using a two-sided $\alpha = .05$.

In addition subgroup descriptive summary tables of change in bone density by subjects with and without 25 hydroxy vitamin D deficiency at baseline (vitamin D deficiency is defined as 25

hydroxy vitamin D < 30ng/ml) will be presented.

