- 16 Activity wrist monitors will be worn by subjects for 7 continuous days after Baseline visit and visit 5 and 7 continuous days before Visits 8 and 11, so that the monitors can be collected at Visit 8 from subjects transferring to the extension study and at Visit 11 from subjects completing FU visit.
- 17 Screening PRO's should be performed no more than 7 days before dosing and may be performed outside of the Screen Visit 2 to meet this timing if required
- 18 Screening DEXA scan will be performed during screening and up to Day 8 after randomisatio. The End of treatment DEXA will be performed only in a case patient reached minimum visit 5(w12) and it can be performed within 14 days before EOT to accommodate scheduling
- 19 The administration of the study drug (BGS649/placebo) will be performed at the study site on Week 12 to allow measurement of PK at pre-dose and 1h post-dose
- 20 SAEs collected from signature of informed consent and AEs, AESIs collected from randomization.

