9.3.3 Rescreening

There are three categories of subjects that may be considered for rescreening:

1. Subjects who met inclusion criteria 3 to 6 at Screening Visits 1, but who were not randomised or received study drug, may be rescreened at a later date.
2. Subjects who failed screening due to an inclusion/exclusion criterion or other study requirement that has been changed through a protocol amendment may also be rescreened at a later date

3. Subjects who failed inclusion criteria 3 to 6 at screening ≥ 6 months previously, and where the clinical situation has changed so that in the investigators judgement they may now meet the criteria may also be rescreened. To include where there was screen failure on total testosterone inclusion criterion through clinically discrepant results ($>100\text{ng/dl}$ difference between tests with one test being $\leq 200\text{ng/dl}$).

Prior to rescreening, every case has to be discussed and approved by Medical Monitor. Rescreening is allowed only one time per screened subject. Rescreened subjects will receive a new Screening number. Previous Screening numbers will not be reused. Rescreened subjects will need to repeat complete Screening assessment (except bone mineral density measured by DEXA if it still falls within 6 months of rescreening visit) starting with signing the ICF.

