9.3.7 Study Drug Interruption and Discontinuation

Subjects may voluntarily discontinue investigational treatment for any reason at any time.

At the time of study drug discontinuation, the subject should have (as soon as possible) an EOT visit with the assessments that are normally done at the Week 24 visit (this should take place within 7 days of discontinuation of study drug). In addition subjects who discontinue the study drug are expected to complete the 12 week follow-up period (Visits 9, 10 and 11) to collect safety data. Subjects who have discontinued before Week 12 (Visit 5) are not required to have EOT DEXA scan measured. The subjects will in addition provide semen sample for PK analysis at Visits 8 (EOT), unless they are not able to provide the samples. This applies also to a subject discontinued because of elevated testosterone as determined by an unblinded physician and if the whole treatment arm is discontinued because of elevated testosterone level as determined by DMC. The investigator and study staff must discuss with the subject, the subject's continued participation in the study and request subjects to continue attending follow-up visits according to the study visit schedule. A study arm may be discontinued from the treatment at the Week 4 visit as decided by DMC during interim analysis (see [Section 9.1](#)). Discontinued subjects will not be replaced. Those subjects will attend only Visit 8 (EOT) and will be followed at FU-Visits 9, 10 and 11 (to 12 weeks after EOT).

The only exception to this requirement is when a subject withdraws consent for all study procedures including post-treatment study follow-up or loses the ability to consent freely (i.e., is imprisoned or involuntarily incarcerated for the treatment of either a psychiatric or physical illness).

If the subject cannot, or is unwilling to attend the follow-up visits, the site staff should request maintenance of regular phone contact with the subject, or with a person pre-designated by the subject. This phone contact should preferably be performed according to the study visit schedule. Data concerning the subject's health status, including information regarding new/concomitant treatments, AEs, AESIs, i.e., rash and vital status will continue to be collected.

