8.1.5 Definition of Baseline

For summary purposes, the baseline value will be defined as the last non-missing value collected prior to the first dose of study medication, unless other specified.

Change from Baseline is defined as (value at assessment date – baseline value).

For Actigraphy Derived Activity and Sleep Parameters, as data is not collected prior to administering the study drug, data collected during the 7 days from Visit 1 will be considered baseline data for all associated analysis.

For Semen quality analysis/parameters, samples at baseline can be taken up to 48 hours after the Baseline Visit. As such baseline will be defined as the last non-missing value collected up to 48 hours post the date of first dose of study medication.

For DXA parameters, assessments at baseline can be taken up to day 8 after the Baseline Visit. As such baseline will be defined as the last non-missing value collected up to 8 days post the date of first dose of study medication.

For selected renal parameters change from Screening will be calculated. Change from Screening will be defined as (value at assessment date – screening value), where the screening value is defined as the last non-missing value collected at a Screening Visit (Day -28 to Day -1).

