Appendix F – DEXA Visit Windows

Visit	Window Start	Window End	Target Day
Baseline	Day -28	Day 8	Day 1
Week 24	Day 140	Day 196	Day 168

Where Day 1 is first dose of study medication

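### The SAP's only post-baseline DXA window has no place for end-of-treatment scans that the protocol requires from men who stop between Week 12 and about Week 20

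*SAP*

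**What the plan says.** **Which scans are required.** Protocol 9.3.7 asks a man who stops study drug to attend an EOT visit within 7 days, with the assessments normally made at Week 24. It makes one exception for bone density: "Subjects who have discontinued before Week 12 (Visit 5) are not required to have EOT DEXA scan measured". Footnote 18 to Table 9-1 in Protocol 9.1.2 sets the same condition and allows the scan up to 14 days before EOT. The SAP's own schedule repeats that footnote.

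**Which scans are analysed.** SAP 8.7.6 says that site-read and over-read data for all statistical analysis will "utilise the visit windows specified in Appendix F". The only post-baseline row there reads "Week 24 Day 140 Day 196 Day 168" (start, end, target), and the footnote adds "Where Day 1 is first dose of study medication". There is no early-termination row. SAP 7.2.1 presents observed cases without imputation unless otherwise specified.

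**Baseline.** The Appendix F row reads "Baseline Day -28 Day 8 Day 1". SAP 8.1.5 has no lower limit: "baseline will be defined as the last non-missing value collected up to 8 days post the date of first dose". Protocol 9.3.3 requires rescreened men to repeat all screening assessments "except bone mineral density measured by DEXA if it still falls within 6 months of rescreening visit".

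SAP section 9 lists only the vitamin D cut-off as a change from the protocol.

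**The concern.** Protocol 9.2 names loss of bone density as a class effect of aromatase inhibitors, and change in bone mineral density is a listed safety endpoint. The protocol asks men who stop after Week 12 for one more scan. The SAP then gives many of those scans no analysis time point, without saying so and without giving a reason. The visit label does not rescue them, because 8.7.6 assigns scans by day and not by visit name.

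The SAP treats testosterone differently. Section 7.1.3.1 defines an end-of-treatment value that uses the last on-treatment assessment for men who stop early. Bone density has no counterpart, although SAP 8.7 bases all safety analyses on everyone dosed.

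The omitted men may not be a random subset. Protocol 9.3.7 makes fragility fracture a mandatory reason to stop, so a man who stops at Week 16 for a fracture would have his scan taken and then left out of every bone density table.

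**Working it through.** **1. The SAP's window.** 24 × 7 = 168, the stated target day. 168 − 28 = 140 and 168 + 28 = 196, the stated limits. The window therefore runs from Week 20 to Week 28.

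**2. Which stops fall outside it.** Week 12 is taken as Day 85 and the end of treatment as Day 168, which gives 84 possible stop days with a required scan. The scan is taken 0 to 7 days after stopping.

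| Stop day | Number of days | Scan in Day 140-196? |
|---|---|---|
| 85-132 | 48 | Never (latest scan 132 + 7 = 139) |
| 133-139 | 7 | Depends on scan date |
| 140-168 | 29 | Yes |

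Between 48/84 = 57% and 55/84 = 65% of these stop days give a scan with no analysis time point. The Week 20 edge is soft. The 14-day allowance before EOT can put a scan for a stop just after Day 140 outside the window, and an EOT visit later than 7 days could bring one in.

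**3. How many scans.** The documents give no dropout rate. Assumption: stops are spread evenly over 168 days, with overall dropout d of 10%, 20% or 30%.

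- Left out per arm = 67 × d × 48/168 to 67 × d × 55/168
- In the Week 24 ANCOVA = 67 × (1 − d) + 67 × d × 29/168 to 67 × (1 − d) + 67 × d × 36/168
- With every required EOT scan used = 67 × (1 − d) + 67 × d × 84/168

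| d | Left out per arm | Left out of 268 | In Week 24 ANCOVA, per arm | With all EOT scans, per arm |
|---|---|---|---|---|
| 10% | 1.9-2.2 | 7.7-8.8 | 61.5-61.7 | 63.7 |
| 20% | 3.8-4.4 | 15.3-17.5 | 55.9-56.5 | 60.3 |
| 30% | 5.7-6.6 | 23.0-26.3 | 50.4-51.2 | 57.0 |

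The last two columns assume that every man has a usable baseline scan and that those who complete treatment are scanned. Men who stop before Week 12 (half of all stops under this assumption) have no scan under the protocol's own rule.

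**4. Direction.** The documents give no bone density SD and no loss by exposure time. For illustration only, let completers change by −1.0% and let a share f = 0.10 (about 7/67) be early stoppers with mean change s. The mean over all scanned men is (1 − f) × (−1.0) + f × s. With s = −3 it is −0.90 − 0.30 = −1.20%. With s = 0 it is −0.90 + 0 = −0.90%. Leaving these scans out can therefore understate or overstate the loss.

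**5. Baseline.** The 6 months run from the rescreening visit. If that visit is on Day −28 and 6 months is taken as 182 days, a carried-over scan can date from −28 − 182 = Day −210. Appendix F rejects it, SAP 8.1.5 accepts it, and without it the man has no change score.

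**The case against.** **Week 24 is the planned time point.** Protocol 13.5.5 summarises DEXA change at Week 24, and a window of 28 days either side is already generous. Keeping a Day 85 scan out of a Week 24 estimate is sound. This stands, and it is why the Week 24 row should not change. It does not explain why a required scan has no other row.

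**Cases are not lost.** A reader might infer that new osteoporosis in early stoppers would disappear. The documents do not support that. Protocol 12.1.7 makes osteoporosis or low density on DEXA, and fragility fracture, events of special interest. SAP 8.7.1 tabulates and lists treatment-emergent ones, and SAP 8.1.7 lists all relevant subject data. What goes missing is the bone density summary, not the report of the case.

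**The planned table need not look too favourable.** A reader might also infer that early stoppers lose more bone, so that the planned table understates harm. No figure in the documents supports this. Protocol 9.2 reports no demonstrated density effect at 12 weeks in the earlier male study and says the present study may be too short to detect one. Shorter exposure could mean smaller losses.

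**Part of the restriction belongs to the protocol.** It asks for no scan from men who stop before Week 12, so the SAP window is not the only reason the analysis leans towards men who stay. Bone turnover markers measured at Week 12 enter an MMRM (SAP 8.6.4.4), so later stoppers do contribute to some bone analysis. Protocol 13.5.1 calls all analyses exploratory.

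**The baseline conflict is narrow.** It touches only rescreened men with a carried-over scan. Rescreening is allowed once, with Medical Monitor approval, and SAP 8.1.5 would keep the scan. It is a conflict between two rules, not a shown loss of data.

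**Conclusion.** The point holds for EOT scans. After a stop on Day 85 to 132 a required scan always falls outside Appendix F if the 7-day rule is met; after a stop on Day 133 to 139 this depends on the scan date. Such scans enter no bone density summary, shift table or ANCOVA. Under even timing of stops and 10-30% overall dropout, that is about 2-7 scans per arm of 67; the true number cannot be fixed from the documents. The direction of any bias is unknown, and the safety reporting of individual cases is intact. The baseline conflict is real but secondary. The change is worth making because it uses safety scans already required, costs little and leaves the planned Week 24 analysis as it is.

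**What to change.** - **Week 24.** Keep Day 140-196 for the Week 24 row and its ANCOVA.
- **End of treatment.** In SAP 8.7.6 and Appendix F, add a row holding each man's last scan from Week 12 on, including early EOT scans. Show it in the descriptive and shift tables with the scan day, and run a supportive ANCOVA on it.
- **Baseline.** Adopt one rule in SAP 8.1.5 and Appendix F that accepts the scans the protocol accepts, with the 6 months for rescreened men counted from the rescreening visit.

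The cost is SAP wording, one row per table and one supportive model, settled before unblinding. No scan or visit is added. The drawback is that the new row mixes exposure durations, so it should be read beside the Week 24 row and not in its place. The baseline rule may also admit older scans, made before the current amendment tightened the DEXA procedures.

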8.8 Other analysis

8.8.1 DMC

An independent, unblinded external DMC will periodically review accumulating safety data. This will include data evaluation of accumulating unblinded safety data of BGS649, testosterone monitoring assessment and performing the interim analysis. Full details of composition, operational aspects, and data to be reviewed and recommendation of the DMC is provided in a separate DMC charter and DMC SAP.

8.8.1.1 Testosterone Monitoring

To ensure adequate safety monitoring, serum total testosterone levels will be evaluated at each visit by an independent unblinded physician and if subject meets discontinuation criteria (total testosterone is ≥ 1500 ng/dL (52 nmol/L) at any 2 consecutive time points during the study), the subject will be discontinued from treatment. In addition, if one of the active BGS649 study arms presents with ≥ 2 subjects meeting this discontinuation criterion at any time point within the first 24 randomized subjects to that arm or $> 15\%$ subjects meet this criterion at any time point ≥ 25 randomized subjects, then the arm will be evaluated by an independent unblinded, external DMC for potential dosing discontinuation based on FDA guidance (FDA Advisory Committee Industry Briefing Document Testosterone Replacement Therapy, Sept 2014). Subjects may be discontinued from the study arm and no further randomisation to that arm will be performed.

Any treatment arm discontinued due to this process will still be presented in summary tables however no formal analysis vs Placebo will be conducted.

8.8.1.2 Interim Analysis

An interim analysis was conducted once approximately 100 of overall planned subjects completed their Week 4 visit. The analysis was performed by the independent DMC who reviewed un-blinded data to identify:

1. Any safety signals across the dose groups which would preclude further continuation of dosing
2. Whether an individual arm has met the criteria of $\geq 75\%$ of subjects reaching the normalisation of testosterone (testosterone within or above normal reference range for healthy adult males according to the FDA)
3. Whether in the opinion of the DMC following unblinded review that when the arm is fully recruited it is expected to achieve a $\geq 75\%$ response at Week 24.

Dosing arms which met either criterion 2 or 3 were deemed to be effective. For arms that were determined to be ineffective or unsafe, dosing was to be stopped and no further randomisation to that arm was performed. Subjects assigned to any ineffective or unsafe arm(s) were to be discontinued from the treatment, attend an EOT visit and followed-up for an additional 12 weeks

(FU, Visit 11). Any treatment arm discontinued due to this process would still be presented in summary tables however no formal analysis vs Placebo will be conducted.

Following the results of the Interim Analysis no dose arm was dropped from the study.

8.8.2 PK analyses

Pharmacokinetic samples will be collected as follows:

1. Plasma PK samples will be taken pre-dose and 1h post-dose at Visit 5. At Visit 8 (EOT; Week 24) it will be taken only once.
2. Semen samples for seminal fluid PK will be taken at Visit 8 (EOT)

This plan does not address the PK analyses of BGS649 (Nonlinear mixed effects modelling will be utilised to develop a population PK model for BGS649 plasma concentrations and to develop a PK/PD model linking BGS649 plasma concentrations to changes in testosterone levels). These analyses will be performed by ICON Pharmacokinetics, Pharmacodynamics, Modelling and Simulation Department and will be described in a separate analysis plan. Results from the PK/PD modelling will be reported separately from the CSR.

BGS649 PK plasma concentrations will be summarised for the PK population by descriptive statistics by treatment regimen and time-point, and including the geometric mean and coefficient of variation.

A graphical representation of the PK plasma concentrations distribution using mean plots (mean and SD) will be provided over time per treatment regimen for the PK population. All dose levels will be plotted on the same graph.

8.8.3 Subgroup analysis

To determine the impact of other baseline measures on the primary efficacy analysis the following covariates may be added to the analysis independently and subgroup analysis performed to test for significance:

- Age
- BMI
- Other baseline parameters reviewed at the classification meeting

All parameters to be tested will be documented at the classification meeting prior to unblinding.

8.8.4 Association Testing

To determine any correlation between endpoints at Week 24, various association testing will be conducted using the PP Population. For the below sets of endpoints scatter graphs will be generated annotated with the coefficient of determination (R^2 statistic):

- Total testosterone vs PRO scores (total and domain)
- Total oestradiol vs PRO score (total and domain)

- Testosterone/oestradiol vs PRO scores (total and domain)
- Activity parameters vs PRO scores (total and domain)
- Sleep parameters vs PRO scores (total and domain)
- Change in grip strength vs PRO scores (total and domain)
- Change in total testosterone vs Change in Grip Strength
- Change in BMI vs Change in Grip Strength
- Change in waist Circumference vs Change in Grip Strength
- Change in bio impedance parameters vs Change in Grip Strength
- Total testosterone vs cardiometabolic parameters: SBP and DBP, lipid panel (total cholesterol, LDL, triglycerides and HDL), HbA1c, fasting glucose and insulin, HOMA-IR and hs-CRP
- Change in BMI vs cardiometabolic parameters: SBP and DBP, lipid panel (total cholesterol, LDL, triglycerides and HDL), HbA1c, fasting glucose and insulin, HOMA-IR and hs-CRP
- Change in waist circumference vs cardiometabolic parameters: SBP and DBP, lipid panel (total cholesterol, LDL, triglycerides and HDL), HbA1c, fasting glucose and insulin, HOMA-IR and hs-CRP
- Change in semen parameters vs Change in LH and FSH levels
- Change in semen parameters vs Change in oestradiol
- Change in systolic blood pressure vs Total Testosterone, Oestradiol and Testosterone/Oestradiol ratio (at Week 12 and Week 24)
- Change in diastolic blood pressure vs Total Testosterone, Oestradiol and Testosterone/Oestradiol ratio (at Week 12 and Week 24)
- Change in Creatinine vs Blood Pressure (Absolute systolic and diastolic blood pressure)
- Change in Creatinine vs Change in Blood Pressure (Systolic and Diastolic blood pressure)

8.8.4.1 PROMIS SexFS Domains Testing

End of treatment testosterone levels (<300ng/dL vs 300-500 ng/dL vs >500 ng/dL) will be tested against each PROMIS sexFS domain score (excluding the domain “interfering factors”) by a MMRM model. Analyses will include the fixed, categorical effects of end of treatment testosterone level, visit, and end of treatment testosterone level-by-visit interaction, as well as the continuous, fixed covariates of the associated baseline value and baseline-by-visit interaction. An unstructured covariance matrix will be used to model the within-subject errors. The end of treatment testosterone factor effect p-value as well as the Week 24 least square mean differences and 95% CI of the pairwise comparisons of each end of treatment testosterone level group will be presented.

This process will be repeated to test the association of baseline testosterone level (<200 ng/dL vs >200 ng/dL) against the change from baseline of each PROMIS sexFS Domain (excluding the domain “interfering factors”).

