To date, BGS649 has also been administered to 21 obese men with HH (8 subjects were assigned to placebo) and was found to be well tolerated without drug discontinuation or drug related serious adverse events (SAEs) (Study CBGS649A2204). This first-in-man study was a 2-part study over 12 weeks (11 treatments); Part 1 was an open-label dose finding study (weekly, individually titrated doses) and Part 2 used a fixed dose regimen (0.3 mg loading dose followed by 10 weekly fixed doses of 0.1 mg). Overall, BGS649 treatment (n=21) resulted in normalisation and maintenance of serum total testosterone, with no evidence of total testosterone peaks above the upper limit of normal (ULN). There were few SAEs reported (only during Part 2 and not considered related to the study drug) and the most commonly reported adverse events (AEs) included spontaneous penile erection and headache. Oestradiol levels were reduced by approximately 25-50% on average and gonadotropin levels (follicle stimulating hormone [FSH] and luteinising hormone [LH]) were increased in subjects treated with BGS649 (no effect observed for subjects on placebo). At the time of the interim analysis of Part 1, new data (Jones et al 2011) indicated that the variances of the homeostatic assessment of insulin resistance (HOMA-IR) were larger than assumed in the original sample size calculations and this (along with the discovery of dosing errors) contributed to the decision for early termination of Part 2 of the study.

A complete review of data obtained to date on BGS649 is presented in the most recent Investigator's Brochure (IB) and Food and Drug Administration (FDA) guidelines have been published on the use of testosterone replacement therapy (Testosterone Replacement Therapy, 2014).

This dose-ranging study aims to demonstrate the efficacy of BGS649 to normalise testosterone (to within normal lab-specific reference range i.e., total testosterone levels 300-1000 ng/dL [10.4-35 nmol/L]) in $\geq 75\%$ of a population of obese male subjects with HH after 24 weeks of double-blind treatment compared to placebo. Study CBGS649A2204 demonstrated that testosterone levels normalised within 2 to 4 weeks of dosing. However, any impact of testosterone levels on the symptoms and signs of hypogonadism is expected to take longer. Therefore, this study evaluates the normalisation of testosterone levels as a primary endpoint, along with key secondary/exploratory endpoints of clinical efficacy after 24 weeks.

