8.6.1 Analysis methods

For binary outcomes the proportion of subjects with a response will be summarised and compared between treatment regimens using Fisher's Exact Test.

For all continuous outcomes, where appropriate, a mixed model repeated measure model (MMRM) analysis will be performed. Analyses will include the fixed, categorical effects of treatment, visit, and treatment-by-visit interaction, as well as the continuous, fixed covariates of the associated baseline value and baseline-by-visit interaction. An unstructured covariance matrix will be used to model the within-subject errors. If the model with the unstructured covariance matrix fails to converge, other covariance structures, including Toeplitz, compound symmetry, and spatial power, will be considered. The denominator degrees of freedom will be calculated according to the Kenward-Roger method. Significance tests for treatment differences (individual BGS649 doses vs. Placebo and between BGS649 doses) will be based on least-squares means.

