8.8.4.2 IIEF Erectile Function Domain Testing

End of treatment testosterone levels (<300ng/dL vs 300-500 ng/dL vs >500 ng/dL) will be tested

against IIEF erectile function domain response of achieving a minimal meaningful difference at Week 24 by a logistic regression model. The end of treatment testosterone factor effect p-value as well as the odds ratio and 95% CI of the pairwise comparison of each end of treatment testosterone level group will be presented.

This process will be repeated to test the association of baseline testosterone level (<200 ng/dL vs >200 ng/dL) against IIEF erectile function domain response of achieving a minimal meaningful difference.

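### The end-of-treatment testosterone models in SAP 8.8.4.1 and 8.8.4.2 pool the four arms without a regimen term, so part of any drug effect not acting through testosterone would appear as a testosterone association

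*SAP*

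**What the plan says.** SAP 8.8.4.1 tests end-of-treatment testosterone in three classes (below 300, 300–500 and above 500 ng/dL) against each PROMIS SexFS domain, interfering factors excepted, by MMRM. The model sentence reads "Analyses will include the fixed, categorical effects of end of treatment testosterone level, visit, and end of treatment testosterone level-by-visit interaction" and continues "as well as the continuous, fixed covariates of the associated baseline value and baseline-by-visit interaction". That list appears complete, and regimen is not in it.

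SAP 8.8.4.2 tests the same classes "against IIEF erectile function domain response of achieving a minimal meaningful difference at Week 24 by a logistic regression model". Its stated output is "The end of treatment testosterone factor effect p-value as well as the odds ratio and 95% CI of the pairwise comparison" for the testosterone classes. No other covariate is named.

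The parent section, 8.8.4, says that "various association testing will be conducted using the PP Population" and gives no split by arm. SAP 8.8.1.2 records that no arm was dropped at the interim analysis, so four arms are pooled.

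The general efficacy model in SAP 8.6.1 has the same layout but names the randomised factor: "Analyses will include the fixed, categorical effects of treatment, visit, and treatment-by-visit interaction". In 8.8.4.1 testosterone class stands where treatment stood; it is not added to it.

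Both sections repeat the process with baseline testosterone (below versus above 200 ng/dL).

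**The concern.** Men enter with total testosterone below 300 ng/dL on two samples (Protocol 9.3.1), and the sample-size section assumes 90% normalisation on an effective dose against a 75% goal. Men on placebo should therefore fall mostly in the lowest class and men on active drug mostly in the upper two. Regimen determines class, and it may also act on sexual function by another route. If it does, a model without regimen credits part of that action to testosterone.

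The documents give one candidate route. Protocol 7.1 reports for the earlier study in obese men that "Oestradiol levels were reduced by approximately 25-50% on average". SAP 8.8.4 also plots oestradiol against patient-reported scores, so the plan itself treats oestradiol as a possible correlate.

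What is at stake is how the class p-values, mean differences and odds ratios are read. A reader would take them as evidence that men who reach higher testosterone feel better, when they may partly restate drug versus placebo.

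**Working it through.** **1. The plan's own figure.** SAP section 5 gives 67 per dose group: goal 75%, true rate 90%, one-sided 2.5%, power 85%. The exact binomial test at n = 67 rejects at 58 or more responders, with alpha 0.0160 and power 87.1%. The continuity-corrected normal approximation gives N = 66.3, rounded up to 67, with power 85.5%. The figure reproduces. It is used here only as the number per arm.

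**2. How much of a non-testosterone drug effect leaks.** Take three active arms to one placebo arm. Let a and p be the proportions at or above 300 ng/dL on active and placebo. Suppose the drug shifts the score by d on every active arm and testosterone has no effect. The expected difference between men at or above 300 and men below 300 is d × share, where

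share = 3a/(3a + p) − 3(1−a)/[3(1−a) + (1−p)].

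The values a = 0.75 and 0.90 come from SAP section 5. The placebo rate is not given, so p = 0.05 to 0.30 is assumed.

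- a = 0.90, p = 0.05: 0.982 − 0.240 = 0.742
- a = 0.90, p = 0.10: 0.964 − 0.250 = 0.714
- a = 0.75, p = 0.10: 0.957 − 0.455 = 0.503
- a = 0.75, p = 0.30: 0.882 − 0.517 = 0.365

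So about 36–74% of the effect appears as a testosterone difference.

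**3. Binary version, for 8.8.4.2.** Assume response of 25% on placebo and 40% on active (drug odds ratio 2.0) and a true testosterone odds ratio of 1.0. At a/p = 0.90/0.10, response is 0.964 × 0.40 + 0.036 × 0.25 = 0.395 at or above 300, and 0.250 × 0.40 + 0.750 × 0.25 = 0.2875 below 300. The pooled odds ratio is (0.395/0.605)/(0.2875/0.7125) = 1.62. It is 1.39 at 0.75/0.10 and 1.27 at 0.75/0.30.

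**4. False rejection of the three-class test.** This is a single-visit linear model with an F-test at 5%. Assumed end-of-treatment means are 270/400/480/560 ng/dL with SDs 80/130/150/160, which put about 35%, 78%, 88% and 95% of the arms at or above 300. The drug shift is equal on all active arms, with no within-arm association. Ranges are across repeated runs.

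| Assumed shift | 67 per arm, no regimen | 40 per arm (assumed), no regimen | With regimen |
|---|---|---|---|
| 0.3 SD | 16–17% | 11–12% | about 5% |
| 0.5 SD | 37–39% | 24–25% | about 5% |
| 0.7 SD | 65% | 43–45% | about 5% |

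A separate simulation was driven by normalisation rates and adjusted for baseline score, at 67 per arm with a/p of 0.90/0.10, 0.75/0.10 and 0.75/0.30. It gave 28%, 17% and 10% at 0.3 SD, and 66%, 40% and 23% at 0.5 SD. With regimen added, rejection was 4–6%.

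**5. Why 67 is an upper figure.** The population is per-protocol. Men enrolled under protocol version 2.0 were not required to complete PROMIS SexFS (SAP 8.6.4.5). A SexFS domain is not calculated if any of its items is missing or scored 0 (SAP 7.1.3.4). The loss cannot be computed from the documents, hence the assumed 40.

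**6. Cost of adjusting.** Suppose the effect acts purely through class, at 0.5 SD for above 500 versus below 300 with the middle class half-way. Under the distributions in step 4, power falls from about 80% to 58% at 67 per arm when regimen is added. In the separate simulation, the SD of that contrast rises from about 0.155 to 0.23 (0.90/0.10) and from about 0.15 to 0.18 (0.75/0.10).

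**7. Baseline-testosterone repeats.** Arm is randomised independently of baseline testosterone. Without regimen, the simulated false-positive rate stays at about 5%.

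**The case against.** The strongest reply is that the objective asks only for any associations between objective findings, testosterone among them, and patient-reported scores (Protocol 8.4, item 6). A pooled marginal association answers that. Regimen is also the intended cause of higher testosterone, so conditioning on it discards the randomised contrast and leaves non-randomised variation within arms. Both points stand. They are reasons to keep the pooled model and show the adjusted one beside it, not to replace it. A reader might infer that the pooled results say nothing about testosterone; the documents do not support that, because they describe the overall association the objective asks for.

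A second reply is that other analyses cover the gap. SAP 8.6.4.5 repeats the treatment MMRM within end-of-treatment testosterone classes for the IIEF and SexFS domains, and SAP 8.8.4 plots oestradiol and the testosterone/oestradiol ratio against the scores. These help interpretation but do not change what the p-values and odds ratios in 8.8.4.1 and 8.8.4.2 measure.

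Third, no document links the oestradiol fall to a patient-reported score or supports a shift of 0.3–0.7 SD outside testosterone. That is correct; the shifts are assumptions. The LH and FSH rise should not be offered as another such route, because Protocol 9.2 describes it as the way testosterone is raised.

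Finally, for 8.8.4.2 the missing term is read from silence, whereas 8.8.4.1 gives an explicit list.

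**Conclusion.** The point holds for the end-of-treatment models. As written, they cannot separate a testosterone association from the part of a drug effect that bypasses testosterone. About 36–74% of such an effect would appear under the testosterone label. The class test would reject in about 17–65% of trials at 67 per arm, or about 11–45% at 40 per arm, for shifts of 0.3–0.7 SD. These sizes rest on assumed placebo normalisation, testosterone distributions and drug shifts, and on a single-visit simplification of the MMRM.

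Two stronger readings are tempting. One is that all of any non-testosterone drug effect is reported as testosterone; the leakage is partial. The other is that the baseline-testosterone repeats share the fault; they do not, because arm is randomised.

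The analyses are exploratory and the primary result is untouched. This is a cheap improvement, not a flaw in the trial's main conclusions.

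**What to change.** For the end-of-treatment testosterone models only, report a second version beside the planned pooled one: add regimen and regimen-by-visit to the MMRM in 8.8.4.1, and regimen to the logistic model in 8.8.4.2. State in 8.8.4.2 which covariates the planned model contains. Base any statement about testosterone beyond the drug-versus-placebo contrast on the adjusted version. Leave the baseline-testosterone repeats as they are.

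The change needs no new data, only one added factor (with its visit interaction in the MMRM) and one more set of output. The price is precision, as in step 6 of the working. The adjusted estimate rests only on non-randomised differences between men within an arm, so the report should say that it is not causal and that a non-significant adjusted result is weak evidence against a testosterone effect.
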